9.7.2.3 Determine the effect of empagliflozin compared to DPP4i on outcomes

Analysis: The effect of empagliflozin compared to DPP4i on outcomes will be assessed using Cox proportional hazards models in a 2-arm comparison. The analysis will include all patients with a valid overlap weight and will be done for overall and within DKD subgroups. The main analysis will assess outcomes while patients remain on initial treatment.

Follow-up will start the day after the index date (date of initiation of empagliflozin or DPP4i) and will continue until the first occurrence of the outcome of interest, or end of study date (date of death, date of study end, 2 years after index date). For the main AT analysis, follow up will be censored early if an empagliflozin user starts a DPP4i or other type of SGLT2i, or if a DPP4i user starts any SGLT2i. For the AT analysis, if an empagliflozin or DPP4i user initiates a GLP1RA, this will be adjusted for in the model using a time-dependent indicator

variable. Additionally, follow-up will be censored early if there is no indication of a new prescription in the year (+30 days) following the last observed prescription.

Incidence rates will be computed as the number of first events per 100 patient years of follow-up. Analyses of time to first event will be performed using Cox proportional hazards models. Outcomes where death is a competing risk will be analyzed using cause-specific proportional hazards models, achieved by censoring follow-up at the time of death. All analyses will be adjusted for covariates (variables) that continue to be unbalanced after reweighting, with any additional covariates that might be of medical interest identified by the clinicians. Hazard ratios comparing empagliflozin to DPP4i with 95% confidence intervals and the adjusted two-sided p-values for superiority testing will be presented for all outcomes.

Kaplan-Meier curves will be created for each outcome in the overall and DKD subgroups using the reweighted population. Kaplan-Meier curves will also be generated to summarize the cumulative incidence of treatment switching by comparator arm.

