		
during the 12 months preceding the index date, i.e.,
 
 ○ For the primary comparison of initiation of empagliflozin versus DPP4 inhibitors, patients will not have any prescription for empagliflozin/any SGLT2i or DPP4 inhibitors during the preceding 12 months. ○ For the comparison of initiation of SGLT2i versus GLP1RA, patients will not have any prescription for SGLT2i or GLP1RA during the preceding 12 months. 
Exclusion criteria:
 
 - Aged <18 years on the first prescription date of the qualifying prescription, - Pre-existing diagnosis of Type 1 diabetes (T1D) during the 12 months before the index date, - Having a disqualifying diagnosis during the 12 months before the index date, defined as having at least one of the following: estimated glomerular filtration rate (eGFR) <30, dialysis, polycystic kidney disease or a kidney transplant, - <12 months of available data before the index date, and/or no complete history of drug prescriptions/or other records of drug use during this period, defined as not having at least 1 ambulatory visit and at least 1 medication prescription during the preceding 12 months, and - Missing or ambiguous data on serum creatinine in the preceding 12 months. 	
Variables:		
Exposure variables will include:
 
 ● Initiation of empagliflozin, GLP1RA, DPP4 inhibitors or any SGLT2i for the treatment of T2D 
Outcomes (evaluated through 24 months after index date):
 
Primary effectiveness outcomes:
 
 ● Composite of a 40% decline in eGFR, incident ESRD, or all-cause death (ACD) 	

Name of company: Boehringer Ingelheim			
Name of finished medicinal product: Jardiance®			
Name of active ingredient: A10BK03 Empagliflozin			
Protocol date: 26 May 2023	Study number: 1245-0228	Version/Revision: 2.0	Version/Revision date: 26 May 2023

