9.2.3 Study visits

Patients will enter the study cohort on the date of their incident prescription for empagliflozin, other SGLT2i or comparator drug (baseline date) during 2014 – 2020. Baseline data will be determined from records at the baseline encounter, and from other health system encounters up to 12 months prior to baseline (see table below for specific look back periods). Follow-up data (relevant medication prescriptions, measurements, and records for determining outcomes) will be collected until 31 December 2021 (study end date), but outcomes will be censored at 2 years after index date or end of data collection, if earlier.

Proprietary confidential information © 2023 Boehringer Ingelheim International GmbH or one or more of its affiliated companies

Table 1 Timing of patient characteristics, clinical information, and follow-up data relative to baseline

	1 Year Prior to Baseline	Baseline	+/- 3 months from baseline	+/- 30 days from baseline	Post baseline
Demographics		X			
Medication Prescriptions	X	X			X
Medical History	X				
Labs			X		X
Vitals				X	
Hospitalization Events					X
Death					X

[figure not shown]

Figure 2 Example exposure period from lookback (12 months pre-index prescription) to the post-index censoring event for a patient in the empagliflozin cohort. Example includes an event of interest (hospitalization) and the censoring time point for new GLP1RA prescription.

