9.5 STUDY SIZE

The estimated required sample size for the primary analysis depends on the incidence rate of the primary composite renal outcome in the reference cohort, and the difference in effectiveness of comparison drugs (hazard ratio, HR) (Table 4). Incidence rates ranging from 13 per 1,000 patient years to 46 per 1,000 patient years (DAPA-CKD SGLT2i cohort) [R21-1080] were considered as representative of anticipated incidence rates in the non-DKD and DKD subgroups. Sample size was estimated to achieve 80% power for a two-sided log rank test with type 1 error of 0.05. Calculations assumed 12 months accrual and 12 months additional follow-up, for a median follow-up of 18 months. Assuming an incidence rate of 30 per 1,000 patient years in the overall cohort, a sample size of approximately N=7,600 per group is estimated to have 80% power to detect a hazard ratio of 0.80. For a subgroup with a higher incidence rate (e.g., 46 per 1,000 patient years), similar power could be achieved with an approximate sample size of N=5,000 per group.

Table 4 Sample size per group, as a function of incidence rate of primary renal outcome and hazard ratio

	Hazard Ratio					
Reference Group Incidence Rate*	0.60	0.65	0.70	0.75	0.80	0.85
13	3843	5178	7264	10771	17316	31648
30	1682	2268	3183	4721	7593	13883
46	1108	1494	2097	3112	5007	9158

* Assumed hazard rate (per 1,000 patient years) in reference cohort

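### Kaplan-Meier is the wrong estimator for absolute-risk curves of outcomes without death and for the cumulative incidence of switching; the excess is small and confined to descriptive curves

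*Protocol*

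**What the plan says.** All the relevant text is in Protocol section 9.7.2.3, which section 9.7.2.4 applies again to SGLT2i versus GLP1RA.

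- Model: "Outcomes where death is a competing risk will be analyzed using cause-specific proportional hazards models, achieved by censoring follow-up at the time of death".
- Outcome curves: "Kaplan-Meier curves will be created for each outcome in the overall and DKD subgroups using the reweighted population".
- Switching curves: "Kaplan-Meier curves will also be generated to summarize the cumulative incidence of treatment switching by comparator arm".
- On-treatment rule in the main analysis: "follow-up will be censored early if there is no indication of a new prescription in the year (+30 days) following the last observed prescription".

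Section 9.2.3 sets the horizon: "outcomes will be censored at 2 years after index date or end of data collection, if earlier". The protocol mentions no cumulative incidence function or other competing-risk display.

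In section 9.3.2 the primary composite and secondary outcomes 5, 7, 8 and 9 include all-cause death. Secondary outcomes 1 to 4 (40% eGFR decline, ESKD, dialysis, transplant), 6 (heart failure hospitalization) and 10 to 15 (safety) do not.

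**The concern.** Censoring at death is a valid way to fit a cause-specific hazard model. It does not give a valid absolute-risk curve. With deaths censored, 1-KM describes the risk that would be seen if nobody died and the event rate stayed the same. It is never below the proportion of patients who actually have the event, and it is above that proportion as soon as deaths precede events. The plan recognises the competing risk in the model and then ignores it in the plots of the same outcomes.

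For switching the mismatch is explicit. The text names cumulative incidence as the target and assigns it an estimator that does not deliver it when patients can die before switching.

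At stake is how the curves are read. Anyone who takes a 2-year risk from a curve for an outcome without death, or a switching proportion from the switching curve, gets a figure that is too high.

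**Working it through.** **Inputs from the protocol.** The horizon is T = 2 years (section 9.2.3). Planning rates for the primary composite are in section 9.5: "Incidence rates ranging from 13 per 1,000 patient years to 46 per 1,000 patient years", with 30 for the overall cohort. The composite includes death, so its rate serves as an approximate ceiling on mortality. Discontinuation requires 1 year + 30 days without a prescription, so it cannot occur before day 395 (395/365 = 1.08 years).

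**Assumptions.** The protocol gives no death, switching or component event rates. The values below are assumed, with constant hazards.

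**The plan's own figures.** There is no figure for any curve to reproduce. The sample-size table that carries the planning rates does reproduce. A Lakatos log-rank calculation (monthly steps, 1 year accrual plus 1 year follow-up, constant hazards) gives 7,593 per group at 30 per 1,000 and HR 0.80, and matches all 18 cells of Table 4 within one patient. Treating the rates as constant hazards is therefore consistent with the protocol.

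**Formulas.** With event hazard r and death hazard d:

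- 1-KM = 1 − exp(−rT)
- Aalen-Johansen cumulative incidence = r/(r+d) × [1 − exp(−(r+d)T)]

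**Renal components, composite rate split evenly (r = d).**

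| Composite rate per 1,000 PY | 1-KM | Cumulative incidence | Excess (points) | Relative |
|---|---|---|---|---|
| 13 | 1.292% | 1.283% | 0.008 | 0.65% |
| 30 | 2.955% | 2.912% | 0.044 | 1.5% |
| 46 | 4.496% | 4.395% | 0.101 | 2.3% |

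**Ceiling on the relative excess.** For given d it is largest when the event is rare, where it tends to dT/[1 − exp(−dT)] − 1. With the whole composite rate taken as death this is 1.3%, 3.0% and 4.7% at 13, 30 and 46 per 1,000. The last is 0.092/[1 − exp(−0.092)] − 1 = 0.047.

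**A more frequent outcome.** At an assumed 100 per 1,000 PY, with death at 10 to 46 per 1,000, 1-KM is 18.13% and the cumulative incidence is 17.95% to 17.34%, an excess of 0.17 to 0.78 points.

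**Arm difference.** At 46 per 1,000 split evenly, with HR 0.80 assumed on both the event and death, the 2-year difference is 0.883 points by 1-KM and 0.847 by Aalen-Johansen, a gap of about 0.04 points.

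**Switching at an assumed 10% per year** (1-KM = 18.13% throughout, death 10 to 46 per 1,000):

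| Competing events | Cumulative incidence | Excess (points) |
|---|---|---|
| Death only | 17.95% to 17.34% | 0.2 to 0.8 |
| Death, plus discontinuation at 15% to 25% per year from day 395 | 17.45% to 16.58% | 0.7 to 1.5 |
| Death, plus 20% stopping at day 395 | 16.40% to 15.88% | 1.7 to 2.2 |
| Death, plus 40% stopping at day 395 | 14.85% to 14.41% | 3.3 to 3.7 |

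The 40% is borrowed from the earlier claims study described in section 9.9. That study measured discontinuation differently, so this row is an illustration only.

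**The case against.** The strongest reply is that no estimate or test changes. The planned results are incidence rates, hazard ratios, confidence intervals and p-values. The cause-specific Cox model is a sound choice, and the primary composite already includes death. Kaplan-Meier beside a cause-specific model is a familiar display, and section 9.7.2.3 uses the term cumulative incidence only for switching. The outcome curves therefore mislead only if read as absolute risks. All of this stands, and it limits the point to presentation.

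A reader might also infer more than the documents support:

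- **That the study will report inflated 2-year risks or distorted risk differences.** Section 9.7.2.3 specifies no 2-year risk and no risk difference as a result.
- **That death rates of 40 to 60 per 1,000 PY should be set beside renal event rates of 20 to 30.** Those totals exceed the 13 to 46 planned for a composite that already contains both.
- **That switching is overstated by 15% to 26%.** That range comes from applying discontinuation and death at a combined 15% to 25% per year from day 0. Starting discontinuation at day 395 at those rates, with death at 10 to 46 per 1,000 throughout, gives about 4% to 9%.
- **That the switching curve is used to judge the as-treated analysis.** The protocol says only that it summarizes switching. Exposure misclassification is examined through the number and timing of prescriptions (section 9.7.1) and the prescribing-data feasibility check (section 9.3.1).

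Finally, discontinuation does not preclude switching as death does, since a patient with no recent prescription can still start the comparator. Counting it as competing is a choice of what the curve should mean. The protocol does not state that choice.

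**Conclusion.** The point holds as a minor correction to descriptive curves. The direction is certain: for the eleven outcomes without death and for switching, 1-KM with death censored is above the actual cumulative incidence once deaths precede events.

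The size is small. At the planning rates the relative excess at 2 years is at most about 4.7%, and it is about 0.01 to 0.10 percentage points for renal components under an even split. For switching at an assumed 10% per year it is 0.2 to 0.8 points from death alone. Discontinuation adds to this only if it is defined as competing, and by how much depends on how many patients stop at about 13 months.

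These sizes rest on constant hazards, on the composite rate as an approximate ceiling on mortality, and on assumed component and switching rates. If observed mortality exceeds the planning range, for example in the DKD cohort, the excess grows with it.

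**What to change.** In section 9.7.2.3, and by reference in 9.7.2.4:

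1. For outcomes that do not include death, replace Kaplan-Meier with overlap-weighted Aalen-Johansen cumulative incidence curves, with death as the competing event.
2. Do the same for treatment switching. If that curve is meant to show switching while on index treatment, also treat discontinuation as competing and say so.
3. Keep Kaplan-Meier for all-cause death and for composites that include death.
4. State that the main-analysis curves remain on-treatment quantities, because switching and discontinuation are still censored there. The change removes the error from censoring death and does not turn them into risks regardless of treatment.

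The cost is one change of estimator, available in SAS and R, the software named in section 9.6. Data, sample size, weights and hazard models do not change.

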9.7.2.4 Determine the effect of SGLT2i compared to GLP1RA on outcomes

Analysis: Repeat objective 3 with the secondary comparison cohort of initiators of any SGLT2i or GLP1RA. In this analysis, follow up will be censored early if a SGLT2i user starts a GLP1RA, or if a GLP1RA user starts any SGLT2i. If a SGLT2i or GLP1RA user initiates a DPP4 inhibitor, this will be adjusted for in the model.

9.8 QUALITY CONTROL

The quality control, review, and monitoring plan are summarized below. Greater details are documented in the study DMRP.

Validation or quality control (QC) refers to establishing by objective evidence that requirements of programming tasks have been implemented correctly and completely. To ensure these requirements are met, internal and beta testing is performed for every query according to applicable standard operating procedures (SOP). Data quality checks will include evaluating variable distributions to identify extreme outliers, which will be handled with input from the [REDACTED] clinical PI. Key variables will be evaluated for unusual patterns of missingness or distributions over time and by site.

A Study Specific Data Characterization (SSDC) query will also be deployed to the selected sites to confirm data availability, completeness, conformance to the CDM specifications and study feasibility prior to the final production query. The SSDC will provide descriptive statistics of the data that will allow for an early evaluation of variable distributions. These results can often provide insights for local institutions to refine their data, and possibly refresh prior to the final query.

Additionally, as part of general QC standards, SAS log files will be saved after each production run and inspected for errors and warnings after each run by the program author. Log files will be free from ERROR messages, and any WARNINGS or problematic NOTES, such as those concerning uninitialized variables or multi-record merging, etc., should be investigated and, if allowed to remain, should be reviewed with the lead statistician, with input from the statistical mentor if needed.

The statistical mentor will review new statistical results before they are released to the internal team, or in parallel (if timelines necessitate), and will review programming specifications and/or code as requested by the lead statistician, or as needed based on an assessment of risk. The [REDACTED] clinical PI will review new statistical results before they are released to the sponsor.

9.10 OTHER ASPECTS

9.10.1 Data quality assurance

A quality assurance audit/inspection of this study may be conducted by the sponsor or sponsor's designees or by Institutional Review Board (IRBs) / Independent Ethics Committee (IECs) or by regulatory authorities. The quality assurance auditor will have access to all medical records, the investigator's study-related files and correspondence, and the informed consent documentation of this study.

10. PROTECTION OF HUMAN SUBJECTS

The study will be carried out in compliance with the protocol, the principles laid down in the Declaration of Helsinki, Guidelines for Good Pharmacoepidemiology Practice (GPP), and the relevant BI Standard Operating Procedures (SOPs). Standard medical care (prophylactic, diagnostic and therapeutic procedures) remains the responsibility of the treating physician of the patient.

The investigator should inform the sponsor immediately of any urgent safety measures taken to protect the study subjects against any immediate hazard, and also of any serious breaches of the protocol.

10.1 MANAGEMENT AND REPORTING OF ADVERSE EVENTS/ADVERSE REACTIONS

The study design involves only the analysis of retrospective data that was collected from the patient records in an aggregate manner. However, if during the study conduct, [REDACTED] incidentally uncovers an adverse event (AE) associated with the use of Empagliflozin or any BI product, that will be reported according to local regulatory requirements for spontaneous AE reporting.

10.2 STUDY APPROVAL, PATIENT INFORMATION, AND INFORMED CONSENT

This NIS will be initiated only after all required legal documentation has been reviewed and approved by the respective Institutional Review Board (IRB)/Independent Ethics Committee (IEC) and Competent Authority (CA) according to national and international regulations. The same applies for the implementation of changes introduced by amendments.

10.3 STATEMENT OF CONFIDENTIALITY

Individual patient medical information obtained as a result of this study is considered confidential and disclosure to third parties is prohibited with the exceptions noted below. Patient confidentiality will be ensured by using patient identification code numbers.

Treatment data may be given to the patient's personal physician or to other appropriate medical personnel responsible for the patient's welfare. Data generated as a result of the study need to be available for inspection on request by the participating physicians, the sponsor's representatives, by the IRB/IEC and the regulatory authorities.

11. PLANS FOR DISSEMINATING AND COMMUNICATING STUDY RESULTS

We will plan to submit both an abstract to a major CV scientific congress, as well as a manuscript to a leading CV peer-reviewed journal. We will also disseminate results to the public using methods endorsed by our stakeholder advisory group.

The rights of the investigator and of the sponsor regarding publication of the results of this study are described in the investigator contract. As a general rule, no study results should be published prior to finalization of the Study Report.

13. ANNEXURES

ANNEX 1. LIST OF STAND-ALONE DOCUMENTS

Number	Document reference number	Description	Date	Title
1	c39368586-01	Study Protocol (V 1.0)	30 June 2022	Comparative cardiovascular and renal effectiveness and safety of Empagliflozin and other SGLT2i in patients with type 2 diabetes (T2D) with and without baseline kidney disease in the United States
2	c39712001-01	Statistical and Epidemiological Analysis Plan (V 1.0)	8 July 2022	Statistical and Epidemiological Analysis Plan (SEAP) for Non-Interventional Study (NIS) to compare cardiovascular and renal effectiveness and safety of Empagliflozin and other SGLT2i in patients with type 2 diabetes (T2D) with and without baseline kidney disease in the United States – Version 1.0

Proprietary confidential information © 2023 Boehringer Ingelheim International GmbH or one or more of its affiliated companies

Number	Document reference number	Description	Date	Title
3	c39712001-02	Statistical and Epidemiological Analysis Plan (V 2.0)	TBD	Statistical and Epidemiological Analysis Plan (SEAP) for Non-Interventional Study (NIS) to compare cardiovascular and renal effectiveness and safety of Empagliflozin and other SGLT2i in patients with type 2 diabetes (T2D) with and without baseline kidney disease in the United States – Version 2.0
4	NA	Data Management and Review Plan	18 July 2022	Comparative cardiovascular and renal effectiveness and safety of Empagliflozin and other SGLT2i in patients with type 2 diabetes (T2D) with and without baseline kidney disease in the United States: Data Management and Review Plan
5	c39712001-02	Study codelist (included with SEAP)	15June2023	1245.0228 Empa DKD Codelist Master with Sources 15June2023

ANNEX 2. ENCEPP CHECKLIST FOR STUDY PROTOCOLS

ENCePP Checklist for Study Protocols (Revision 4)

Adopted by the ENCePP Steering Group on 15/10/2018

The European Network of Centres for Pharmacoepidemiology and Pharmacovigilance (ENCePP) welcomes innovative designs and new methods of research. This Checklist has been developed by ENCePP to stimulate consideration of important principles when designing and writing a pharmacoepidemiological or pharmacovigilance study protocol. The Checklist is intended to promote the quality of such studies, not their uniformity. The user is also referred to the ENCePP Guide on Methodological Standards in Pharmacoepidemiology, which reviews and gives direct electronic access to guidance for research in pharmacoepidemiology and pharmacovigilance.

For each question of the Checklist, the investigator should indicate whether or not it has been addressed in the study protocol. If the answer is "Yes", the section number of the protocol where this issue has been discussed should be specified. It is possible that some questions do not apply to a particular study (for example, in the case of an innovative study design). In this case, the answer 'N/A' (Not Applicable) can be checked and the "Comments" field included for each section should be used to explain why. The "Comments" field can also be used to elaborate on a "No" answer.

This Checklist should be included as an Annex by marketing authorisation holders when submitting the protocol of a non-interventional post-authorisation safety study (PASS) to a regulatory authority (see the Guidance on the format and content of the protocol of non-interventional post-authorisation safety studies). The Checklist is a supporting document and does not replace the format of the protocol for PASS presented in the Guidance and Module VIII of the Good pharmacovigilance practices (GVP).

Section 1: Milestones	Yes	No	N/A	Section Number
